COPD: Comparison of existing prognostic tools for 1 year mortality and assessment of symptom burden to facilitate Advance Care Planning

Scientific Abstract:

Background: Following hospitalisation for an exacerbation of COPD (ECOPD), one year mortality is 23.2%. Compared to inoperable lung cancer, patients with severe COPD have a greater symptom burden but much lower access to palliative care and advance care planning. Improved prognostication will support selection for, and use of, these services.

Aims: To facilitate palliative care and advance care planning in patients surviving hospitalisation for ECOPD, we will: 1) compare the performance of prognostic tools for prediction of one year mortality; 2) assess ease of completion of these tools; 3) assess symptom burden and quality of life over one year.

Methods: In patients with ECOPD surviving to hospital discharge, established prognostic tools and a novel tool (from the PEARL derivation cohort n=824) will be compared for prediction of one year mortality: a) within the existing PEARL validation cohort of 1,593 patients, and b) prospectively in at least 310 patients. Patients will undergo longitudinal assessment of symptom burden and quality of life.

Benefits: This study will identify which prognostic tool performs best for one year mortality outcome in patients hospitalised with ECOPD. This should lead to more frequent and appropriate engagement with palliative care and advance care planning, and prompt timely discussions with patients about end of life planning.

Lay Summary:

Chronic Obstructive Pulmonary Disease (COPD) is a common progressive lung disease which causes breathlessness and frequent exacerbations. During exacerbations patients become more breathless, often requiring hospitalisation. Patients with severe COPD commonly become housebound, lose their independence and suffer significant depression and anxiety. Hospital admissions become increasingly common towards end-of-life; however this also means that hospitalisation is a good opportunity to identify patients at risk of poor outcome. Such patients, when well-informed, may wish to consider alternatives to admission and avoidance of intrusive procedures and treatments. Unfortunately, predicting which patients are likely to die in the near future is particularly challenging in non-malignant disease. Patients with severe COPD have a higher symptom burden than those with incurable lung cancer, yet they are less likely to receive specialist palliative care, or to have engaged in advance care planning (where patients discuss and document their wishes regarding their future care). To improve provision of palliative care services and ensure patients are given the opportunity to make truly informed decisions about their future care, the first step required is accurate identification of those who would benefit.

Well-designed prognostic tools outperform clinician judgement in most settings. We will compare the accuracy of one year mortality prediction, and ease of completion, of several clinical tools in patients who survive an ECOPD requiring admission. This will initially be performed using data collected during previous research (we developed a number of tools now routinely used), then prospectively confirmed in a minimum of 310 patients admitted consecutively with an ECOPD. The latter group of patients will be invited to participate in a follow-up study, assessing symptom burden, quality of life, and readmissions.

We anticipate that this project will improve access to palliative care, and help to facilitate well-informed discussions with patients and their families about their future care. This may include whether they would like to be readmitted to hospital or cared for at home, and which offered interventions they would be willing to accept in hospital. This should ensure better symptom control

and quality of life for patients with severe COPD reaching the end of their life, and empower them to avoid aggressive interventions if preferred. This is all a routine part of care for patients with terminal cancer but is currently often not afforded to patients with non-cancer conditions.

Background:

Exacerbation of COPD (ECOPD) is the second commonest reason for emergency hospital admission in the UK.⁽¹⁾ National audits between 2008 and 2014 show a substantial rise in 90-day readmissions (from 33% to 43%).⁽²⁾ Among those who survive, 23.2% die within 1 year.⁽³⁾

In severe COPD, there is a huge unmet need for appropriate palliative care and advance care planning. Compared to unresectable lung cancer, quality of life (QOL) is worse,⁽⁴⁾ and levels of disability, anxiety and depression greater.⁽⁴⁾ In addition to high symptom burden,⁽⁴⁾ frequent hospital admissions and invasive interventions at the end of life are common.⁽⁴⁻¹⁰⁾ Despite this, advance care planning is rarely addressed, largely reflecting the uncertainty of prognosis in COPD; in malignancy deterioration is more predictable, and engagement with advance care planning and palliative care services is the norm.^{(4, 6, 11,}

¹²⁾ This uncertainty can lead to reluctance from clinicians to involve palliative care services, or to have frank discussions with COPD patients about their future care, to the detriment of their QOL.⁽¹³⁻¹⁵⁾ Among those patients surviving to discharge, disease-specific risk stratification tools have been developed for readmission and death,^(3, 16-19) whilst other non-COPD specific tools may be applicable in this setting.^(20, 21)

Due to time pressures during hospitalisation,⁽²²⁾ the provision of acute care takes precedence over anticipatory planning. Acute, general and respiratory physicians must feel empowered to, and capable of, incorporating palliative care and advance care planning into their own practice,^(8, 12) and a simple prognostic tool should assist with this. Integrating these aspects of care into routine COPD management would be supported by patients.^(6, 8, 23, 24)

Aims:

1. Determine which clinical tool is most appropriate to identify patients at risk of death within one year, in terms of performance and ease of completion, following hospitalisation with ECOPD.
2. Patients surviving beyond one year may have palliative care needs. We will assess quality of life, symptom burden and utilisation of healthcare services in this patient group over one year, and compare to risk groups within the prognostic tool.

There is a pressing need to more accurately identify which patients with ECOPD surviving to discharge are most at risk of adverse outcome, and likely to benefit from advance care planning and palliative care. The findings will be presented nationally and published in an international journal. The project is supervised by two consultant respiratory physicians and a consultant in palliative medicine, and will be primarily conducted by a respiratory palliative care fellow.

Methods:

Comparison of prognostic tools:

The PEARL score predicts readmission or death within 90 days of discharge following ECOPD, and was developed by the lead supervisor's research team.⁽³⁾ Within the PEARL derivation cohort (2 hospitals, 824 patients), they have developed a novel tool to predict one year survival. The performance of this novel tool and existing COPD prognostic tools (BODEX,⁽¹⁷⁾ PEARL,⁽³⁾ COPD PIG,⁽²⁰⁾ CODEX,⁽¹⁶⁾ ADO,⁽¹⁹⁾ DOSE,⁽¹⁸⁾ the non COPD specific SPIC⁽²¹⁾ and the new BARC⁽²⁵⁾) will be compared in the PEARL validation cohort (6 hospitals, 1,593 patients).

Performance of all tools will also be further prospectively assessed in a minimum of 310 patients across two sites. The COPD-PIG is intended to only be scored in patients who the clinician "would not be surprised" if they died within one year; the performance of this tool cannot be fully assessed

retrospectively. Prospective validation will also allow an assessment of the ease of data collection; this is not available for the existing PEARL cohort but is a key consideration in selection of the final tool to ensure it is appropriate for widespread use on hospital wards. Consecutive, unique patients admitted to Northumbria Healthcare NHS Foundation Trust and Newcastle Upon Tyne Hospitals NHS Foundation Trust with ECOPD will be identified. Demographic and clinical indices, including the components of the nine prognostic tools, will be collected. Caldicott and Research and Ethics Committee approval are in place. Hospital readmissions, utilisation of other healthcare services such as the local palliative care teams and Hospice and survival will be assessed over one year. In common with similar studies,^(3, 26-29) this validation study will be non-consenting.

Patients identified as high-risk by the selected tool who survive beyond one year may still warrant palliative care input if their symptom burden is high. The patients enrolled in the validation study will be invited to participate in a consenting longitudinal outcomes study, aiming for at least 50% participation. Symptom burden and functional status will be assessed using the St George's Respiratory Questionnaire (SGRQ),⁽³⁰⁾ Hospital Anxiety and Depression Score (HADS),⁽³¹⁾ Australian modified Karnofsky Score (AKPS),⁽³²⁾ eMRCD score,⁽³³⁾ and modified Borg scale at baseline,⁽³⁴⁾ and 1, 3, 6 and 12 months. The intention is for the baseline and 3 month assessments to be conducted via face to face meetings, and the additional 1, 6 and 12 month assessments to be conducted over the phone; however, in order to maximise the number of participants we will be flexible with home/hospital visits versus telephone interviews according to patient preference. This data will be used both to calculate the relationship between symptom burden and death, and to identify the characteristics of patients who are especially symptomatic.

Inclusion and Exclusion Criteria:

All patients consecutively admitted with ECOPD will be screened.

Inclusion Criteria:

1. Age 35 years or older.
2. Smoking history greater than or equal to 10 pack years.
3. Obstructive spirometry (FEV1/FVC < 0.7).
4. ECOPD primary diagnosis.
5. Survival to discharge.

Exclusion Criteria:

1. Previous inclusion in the study.
2. Malignant neoplasm or other pathology likely to limit survival to less than 1 year.
3. For the longitudinal study only, inability to give informed consent.

Statistical analysis:

The primary outcome of interest is prediction of one year mortality. Assuming a one year mortality rate of 23.2%, (PEARL)⁽³⁾ an area under the receiver operating characteristic (AUROC) curve of 0.70, with a standard error for the AUROC curve of 4%, a minimum sample size of 310 subjects is required (validation cohort).

The characteristics of the cohort will be summarised using standard descriptive statistics appropriate to the level and distribution of the data. Groups will be compared (including by mortality outcome) using standard tests of statistical inference (e.g. t-test, Mann-Whitney U test, Fishers exact test). The performance of candidate prognostic tools will be compared by 1) assessing the positive and negative predictive value within the high-risk groups; and 2) AUROC curve analysis, with performance compared using the method of DeLong et al. Where data imputation is required, this will be done using multiple imputation methods. Statistical significance will be set at 5% throughout. The statistical analysis plan will be finalised prior to end of recruitment to avoid potential bias.

Outcome Measures:

Validation Study:

Primary outcome:

Positive predictive value and sensitivity of the prognostic tools listed for prediction of one year mortality.*

Secondary Outcomes:

1. Ease of completion of prognostic tools assessed by: a) Likert scale; b) missing data.
2. Area under the receiver operating characteristic curve for each prognostic tool.
3. Negative predictive value of the prognostic tools for prediction of one year mortality.
4. Hospital readmission rates at 30, 90 and 365 days.
5. Proportion of patients on the palliative care register and relation to mortality.
6. Utilisation of palliative care services: hospice; community palliative care team.
7. Inter-observer agreement on scoring.

*This is an exploratory study. The optimal tool to identify patients for advance care planning needs to offer high PPV (i.e. the substantial majority of those identified at high risk of dying should not survive beyond one year) and reasonably high sensitivity (i.e. most deaths within one year should be identified). Ease of completion must also be considered as this will strongly influence engagement.

Longitudinal cohort:

In the whole cohort and individual risk groups within the prognostic tools, assess:

1. Baseline SGRQ, HADS, modified BORG, AKPS.
2. Mean change in SGRQ, HADS, modified BORG, AKPS compared to MCID.
3. Duration SGRQ, HADS, modified BORG, AKPS maintained above baseline.
4. Relation between clinically significant anxiety and depression on discharge and survival, QoL, functional status and readmissions.
5. Best prognostic tool to predict poor QoL and/or death within one year, as per positive predictive value and sensitivity.

Patients in a high mortality risk group identified for advance care planning who do not die are not “false positives” if they have a high symptom burden. The proportion of patients with high symptom burden not identified is also clinically relevant.

Ethical Considerations:

To validate a meaningful predictive tool it is essential that patients at the extremes of mortality risk are not selectively excluded. The most unwell patients would be unlikely to be able to consent, introducing a significant selection bias were they to be excluded. In common with previous prognostic tools developed by this group and others,^(3, 26-29) the validation study will not require individual patient consent. All included indices are routinely available and participation will not influence normal clinical care. Mortality and readmission data is tracked electronically in all patients. All records will be anonymised.

All patients surviving to discharge will be invited to partake in a follow up study assessing patient reported QOL. Participation in this part of the study will require written informed patient consent. IRAS approval is in place for the existing cohort (REC: 08/H0905/88 & 12/NE/0379) and for the prospective validation and longitudinal cohorts (REC: 18/NE/0226).

Data Handling:

Caldicott and Research and Ethics Committee approval are in place (REC: 18/NE/0226). Patients in all arms of the study will be identified by the usual care team. Patients must be identifiable to follow up

data queries or insert readmission data. Clinical data will be kept on a password protected server, on a secure database with no patient identifiable information; a separate secure database will contain patients' identifiable information but no clinical details, with ID codes to link patients to their clinical data. Patients' notes will only be reviewed in usual clinical areas or the office of the research fellow. Case Report Forms will be kept in a locked filing cabinet in a locked office accessible by research staff only. Access to patient identifying information will be via trust servers only. Staff will all be NHS employees.

Research Timetable and Management:

Ethical approval is in place (REC: 18/NE/0226). Data collection for the prospective cohort is expected to begin in January 2019. As the prospective prognostic study will be non-consenting, recruiting 310 patients is expected to be fully achieved by summer 2019.

[name] will act as chief investigator. He, [name] and [name] will co-supervise the Respiratory Palliative Care Fellow [name]. [name] undertook the power calculation and will provide on-going statistical support. Financial management, study sponsorship and data monitoring will be provided by Northumbria Healthcare NHS Foundation Trust Medicine department for the first year and Education department for the continuation of the project.

Benefits:

This study will identify which prognostic tool is most appropriate for use in patients hospitalised with ECOPD for 1 year mortality outcome, balancing performance with ease of completion.

Reliable prognostication in ECOPD, based on objective criteria should lead to more frequent and appropriate engagement with palliative care and advance care planning. Timely discussions about end of life planning will be facilitated. Patients will ultimately benefit from informed discussions about their future care, and avoiding future hospital admission when no longer appropriate to their condition and wishes. Such practice is commonplace in incurable cancer, but hitherto often denied to patients with end stage COPD, to their detriment.^(4, 6)

Dissemination of results:

The findings will be disseminated to a broad regional, national and international audience, including respiratory specialists, general physicians and palliative medicine physicians, through presentations at local, national and international conferences, and publication in high ranking, peer-reviewed, journals.

Locally, we will keep patients, carers, primary and secondary care clinicians, healthcare managers, commissioners and neighbouring healthcare providers informed by publications in existing newsletters and presentations at local and regional meetings, conducted within both NHS organisations and the University.

The Chief Investigator (CI) is Chair of the British Thoracic Society COPD Speciality Advisory Group (SAG), which will aid dissemination of the results.

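### Does including COPD-PIG in the 1,593-patient comparison, without the clinician judgement it depends on, undermine the comparison of tools?

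*Combined protocol and SAP*

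**What the plan says.** The Methods, under Comparison of prognostic tools, begin the list of tools with "The performance of this novel tool and existing COPD prognostic tools (BODEX,⁽¹⁷⁾ PEARL,⁽³⁾ COPD PIG" and continue to CODEX, ADO, DOSE, SPIC and BARC. That makes nine with the novel tool. All of them "will be compared in the PEARL validation cohort (6 hospitals, 1,593 patients"). The Scientific Abstract gives the same two settings: "a) within the existing PEARL validation cohort of 1,593 patients, and b) prospectively in at least 310 patients". The Lay Summary describes the retrospective result as "then prospectively confirmed in a minimum of 310 patients admitted consecutively with an ECOPD".

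The next paragraph of the Methods takes all tools into the prospective cohort and adds a caveat: "The COPD-PIG is intended to only be scored in patients who the clinician" would not be surprised to see die within a year. Retrospectively, it says, "the performance of this tool cannot be fully assessed".

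Statistical analysis makes no exception for any tool: "The performance of candidate prognostic tools will be compared by 1) assessing the positive and negative predictive value within the high-risk groups", and by area under the ROC curve (AUROC) with DeLong's method. Outcome Measures, under Validation Study, gives the primary outcome as "Positive predictive value and sensitivity of the prognostic tools listed for prediction of one year mortality".

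The documents do not say how COPD-PIG is scored or labelled in the 1,593 patients. Nor do they say how patients who fail the surprise question are classified prospectively.

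**The concern.** The list of tools and the caveat pull against each other. COPD-PIG is entered in the retrospective comparison on the same footing as the other eight tools, and the plan then says it cannot be fully assessed there. If only its indicators are scored in the 1,593 patients, the two stages report different rules under one name.

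At stake would be COPD-PIG's place among the tools. A clinician's judgement placed in front of a score changes who is flagged, and so changes both PPV and sensitivity. The retrospective cohort is also the more precise of the two, so a shift caused by the missing question could be read as a real difference between tools. A prospective result could then appear to contradict a retrospective one only because the rule had changed.

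**Working it through.** **1. Precision of the two stages.** Inputs from Statistical analysis: AUROC 0.70, mortality 23.2%, target standard error 4%, minimum 310 patients. The Hanley-McNeil formula, with A = 0.70, n₁ deaths and n₀ survivors, is

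SE² = [A(1−A) + (n₁−1)(Q₁−A²) + (n₀−1)(Q₂−A²)] / (n₁n₀), where Q₁ = A/(2−A) = 0.538 and Q₂ = 2A²/(1+A) = 0.576.

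- 310 patients: n₁ = 71.9, n₀ = 238.1, SE = 0.0376.
- 1,593 patients: n₁ = 369.6, n₀ = 1,223.4, SE = 0.0165.

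This formula reaches 4% at 274 patients, so it does not reproduce 310 exactly. At 310 the standard error still rounds to 4% and meets the target. The point at issue does not depend on this figure. The retrospective stage is indeed the more precise.

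**2. What the surprise question does to PPV.** The documents give no cut-off and no pass rates, so the following are assumptions: sensitivity 0.60 and specificity 0.70 for the indicators alone, and answers independent of the score given outcome. Let g₁ and g₀ be the shares of deaths and survivors who pass the question. Per patient in the cohort:

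- true positives = 0.232 × 0.60 × g₁ = 0.1392 g₁
- false positives = 0.768 × 0.30 × g₀ = 0.2304 g₀
- PPV = 0.1392 g₁ / (0.1392 g₁ + 0.2304 g₀)

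| g₁ | g₀ | PPV | Sensitivity, all deaths in denominator |
|---|---|---|---|
| 1 | 1 (question not used) | 0.377 | 0.60 |
| 0.9 | 0.7 | 0.437 | 0.54 |
| 0.7 | 0.4 | 0.514 | 0.42 |
| 0.5 | 0.2 | 0.602 | 0.30 |
| 0.7 | 0.7 | 0.377 | 0.42 |

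PPV rises if flagged deaths pass more often than flagged survivors, and stays put if they pass equally often (last row). The change can be large or nil.

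**3. The direction for sensitivity is not fixed.** The last column keeps every death in the denominator and counts those who fail the question as not high risk. The plan does not state that rule. The other reading is to evaluate COPD-PIG only in patients who pass, since only they are meant to be scored. Under independence, the third row then gives 0.42/0.70 = 0.60, the same as without the question.

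If answer and score are positively related, the direction reverses. Assume normally distributed scores with AUROC 0.70, sensitivity 0.60 without the question, 75% of deaths and 40% of survivors passing, and an answer-score correlation of 0.3. Then 48.8% of all deaths are both flagged and pass:

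- all deaths in the denominator: 48.8%, against 60% without the question;
- deaths who pass in the denominator: 0.488/0.75 = 65%, against the same 60%.

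So the retrospective figure could be too high, about right or too low, depending on a denominator not yet stated.

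**4. Where the primary outcome sits.** The Methods use the term validation study for the prospective cohort followed without consent, and invite its patients to the longitudinal study. The 310 calculation is tagged as the validation cohort. The outcome list under Validation Study includes a Likert rating of ease of completion, and the Methods say ease of data collection is not available for the existing cohort. PPV and sensitivity as the primary outcome therefore belong most naturally to the prospective cohort, where the clinician can be asked.

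**5. How the stages relate.** Only the Lay Summary calls the prospective stage confirmation. The Methods describe it as a further assessment of all tools and place the COPD-PIG caveat directly after introducing it. They also make ease of collection a key consideration in choosing the final tool, so retrospective accuracy alone cannot settle the choice.

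**The case for a change.** The strongest case for a change is that admitting a limitation is not the same as stating a rule. COPD-PIG stays on the list for the 1,593 patients, and Statistical analysis applies predictive values, AUROC and DeLong's test to all candidate tools without separating the cohorts. The prospective stage gives COPD-PIG a proper assessment but does not correct the retrospective one. Two or three sentences would settle the matter, with no new data.

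Part of this stands. The scoring rule, the label and the prospective denominator are unstated, and an unlabelled retrospective result could mislead.

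The rest is weaker. That COPD-PIG will be scored without the question is a sound inference, but the plan's wording is equally compatible with a partial or descriptive result. The effect sizes come entirely from assumed inputs; the 0.70 is a sample-size assumption, not an estimate for COPD-PIG. Removing the tool from the retrospective tests, rather than reporting it there as partial, is a matter of preference.

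**Conclusion.** The tension is real, but the plan has already recognised it and no change is needed. The retrospective COPD-PIG result is probably for the indicators without the surprise question and should be read as partial, which is what the Methods convey. In the illustrations PPV moves by between 0 and 0.23 (0.377 to at most 0.602). Sensitivity moves from 0.60 down to 0.30, or up to 0.65, according to pass rates and denominator. These figures show sensitivity to assumptions and are not estimates of bias.

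The conclusion rests on three readings: that the primary outcome belongs to the prospective cohort, that the question will be recorded there with the other components of the nine tools, and that analysts who wrote the caveat will carry it into the results. Each is well supported, though none is spelled out. The other eight tools are unaffected. Statistical analysis says the analysis plan will be finalised before recruitment ends, which is the ordinary place for the label and the classification rule.

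### Do longitudinal outcomes 2 and 3 need a stated scale direction and a rule for deaths before they can be analysed by mortality-risk group?

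*Combined protocol and SAP*

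**What the plan says.** The outcomes are in the Outcome Measures section, under Longitudinal cohort. The lead-in sets the populations: "In the whole cohort and individual risk groups within the prognostic tools, assess". Item 2 is "Mean change in SGRQ, HADS, modified BORG, AKPS compared to MCID" and item 3 is "Duration SGRQ, HADS, modified BORG, AKPS maintained above baseline". Item 4 relates anxiety and depression at discharge to survival, among other things. Item 5 looks for the tool that best predicts poor quality of life, death, or both.

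The Methods section introduces the instruments with "Symptom burden and functional status will be assessed using the", so the set mixes symptoms with function. Assessments are at baseline and at 1, 3, 6 and 12 months. No section gives a scoring direction or an MCID value.

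The Statistical analysis section has one sentence on missing data: "Where data imputation is required, this will be done using multiple imputation methods". It also says "Groups will be compared (including by mortality outcome) using standard tests of statistical inference", and closes with "The statistical analysis plan will be finalised prior to end of recruitment to avoid potential bias". The footnote to the validation outcomes states: "This is an exploratory study".

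**The concern.** There are two gaps.

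**Direction.** One phrase covers four scales. On their usual scoring (an assumption, because the documents do not give it), a higher value is worse on SGRQ, HADS and modified Borg and better on AKPS. Read literally, item 3 would count time spent worse on three scales and time spent better on the fourth.

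**Death.** Items 2 and 3 are to be reported by mortality-risk group, and such groups lose unequal shares of patients to death by construction. Mean change from available scores describes survivors only. Multiple imputation applied without restriction would create scores for people who had died. If worsening tends to precede death, either approach could make a high-risk group look better than it was. Duration is also cut short by death, and more so in the high-risk group, so a shorter duration there need not mean faster decline.

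What would be at stake is the description of symptom course by risk group. The primary outcome (predictive value and sensitivity for one-year death) and baseline burden (item 1) do not depend on it.

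**Working it through.** The plan gives no figure for items 2 and 3, so there is none to reproduce. The 310 was set for AUROC precision and is used here only as a count.

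**Inputs from the documents:** 310 patients, at least 50% participation, 23.2% one-year mortality, AUROC 0.70 (planning value), visits at 1, 3, 6 and 12 months.

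**Assumptions:** a 15% mortality alternative, because the Ethical Considerations section expects the most unwell to be unable to consent; an equal-variance binormal score; a high-risk group made up of the top 20%; a constant hazard within each group.

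**Deaths.** 310 × 0.50 = 155 participants. 155 × 0.232 = 36.0 deaths, or 155 × 0.15 = 23.3. Under a constant hazard at 23.2%, cumulative deaths by months 1, 3, 6 and 12 are 3.4, 9.9, 19.2 and 36.0. So (36.0 − 19.2)/36.0, about 47%, fall in the last interval (48% at 15% mortality).

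**Mortality by group.** The separation is d = √2 × Φ⁻¹(0.70) = 1.414 × 0.524 = 0.742. The cut-off c solves m[1 − Φ(c − d)] + (1 − m)[1 − Φ(c)] = 0.20.

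- At m = 0.232, c = 1.053 and 37.8% of deaths lie above it. High-risk mortality is 0.232 × 0.378/0.20 = 0.438. In the rest it is (0.232 − 0.0877)/0.80 = 0.180.
- At m = 0.15, c = 0.980 and 40.6% of deaths lie above it. This gives 0.304 and 0.111.

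The high-risk group has 0.20 × 155 = 31 people, of whom 31 × 0.562 = 17.4 (or 31 × 0.696 = 21.6) could have 12-month scores.

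**Time alive.** Mean months alive in the year = 12q/[−ln(1 − q)], where q is the group's one-year mortality.

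- At 23.2%: 9.12 against 10.88, a gap of 1.76 months.
- At 15%: 10.06 against 11.32, a gap of 1.26 months.

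This would be the gap in item 3 only if every patient held the state until death or month 12. If it is held for half the time alive, the gap is 0.88 or 0.63 months.

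**Sensitivity of the gap (months) to AUROC and cut-off:**

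| AUROC | 23.2%: top 10 / 20 / 40% | 15%: top 10 / 20 / 40% |
|---|---|---|
| 0.65 | 1.5 / 1.3 / 1.0 | 1.1 / 0.9 / 0.7 |
| 0.70 | 2.1 / 1.8 / 1.4 | 1.6 / 1.3 / 1.0 |
| 0.75 | 2.9 / 2.3 / 1.8 | 2.1 / 1.7 / 1.2 |

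The range is 0.7 to 2.9 months. It illustrates the scale and is not a bound.

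**Item 2.** No figure can be given. Bias depends on how strongly worsening is linked to death, and the documents say nothing on that. Without such a link there is none.

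**Reading the text on direction.** Item 3 reports each scale in the cohort and in each risk group. It does not compare one scale with another. Within a scale, even the literal reading measures the same quantity in every group. The clash between scales appears only once outside scoring conventions are brought in, and those same conventions tell the analyst which way is better.

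**Reading the text on death.** The imputation sentence is conditional and follows directly on the tool-performance methods; nothing extends it to scores after death. Aim 2 opens with patients who live beyond a year, which makes change among survivors a quantity of interest in itself, although the lead-in to the items refers to the whole cohort. Deaths are tracked electronically for everyone, and mortality by risk group follows from the primary outcome.

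**The case for a change.** The best case for a change runs as follows. The plan says that high-risk patients who survive with heavy symptoms should not count as false positives, so symptom results by risk group bear on how the tools are judged. It also wants a tool whose high-risk patients mostly die within the year. A tool with 60% predictive value and 60% sensitivity (assumed) would flag 0.60 × 36/0.60 = 36 of the 155. About 14 of them (40%) would be alive for a 12-month score, against 105 of 119 (88%) in the rest. A survivor-only mean in that high-risk group describes a minority. Writing the rule costs a few lines, and an analysis plan still open is the moment to write it.

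Much of this stands as description. The text is silent, the loss is unequal, and duration from four visits also needs a derivation rule. What does not follow is that the plan must change. Where the plan needs quality of life and death together to judge a tool, item 5 already combines them. Adding a proportion alive and not worse would overlap with item 5 and be imprecise: with 31 high-risk patients the 95% half-width is 1.96 × √(0.3 × 0.7/31) = 0.16 to 1.96 × √(0.5 × 0.5/31) = 0.18. The remaining steps are to name the direction, label change as among those alive, show deaths beside it and impute only for the living. They are ordinary practice, and the plan points towards them by comparing groups by mortality outcome.

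**Conclusion.** No change to the plan is called for. Both gaps are missing detail in exploratory items, of a kind that analysts fill sensibly when the analysis plan is finalised before recruitment ends. Item 3 most plausibly means better than baseline, and no passage provides for imputing scores after death.

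The unequal loss to death is real: about 36 deaths among 155 participants (about 23 at an assumed 15% mortality) and a modelled difference in time alive of 0.7 to 2.9 months. Those months rest on a binormal score, constant hazards, AUROC 0.65 to 0.75 and cut-offs from the top 10% to the top 40%, and they are not a ceiling. Any bias in mean change cannot be sized from the documents. The primary outcome, baseline burden and the item combining poor quality of life with death are unaffected.
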